7.2 Quality Assurance Audit

Study sites, the study database, and study documentation may be subject to Quality Assurance audit during the course of the study by the Sponsor or designee. In addition, inspections may be conducted by regulatory bodies at their discretion.

The Investigator will promptly notify the Sponsor and designee of any audits scheduled by any regulatory authorities and promptly forward copies of any audit reports/certificates received to the Sponsor.

8.0 STATISTICS

The complete version of the SAP will include all detailed statistical analysis methods, which will be available after the each Data Review Meeting. This statistical section presented below summarizes the SAP.

The first analysis of data will occur after all subjects have completed the assessments scheduled for Day 15. These data will be used to determine the efficacy of treatment with CT-P27 to establish an effect size for subsequent clinical studies. The data will also provide information about the safety and PK (only Subgroup [PK] Cohort) of CT-P27 up to Day 15. An additional analysis will be performed when all subjects have completed the assessments scheduled for Day 110/EOS visit.

8.1 Determination of Sample Size

Randomization will be stratified by flu vaccination history within a year (Yes vs No) and participation in PK sub-study (Yes vs No).

This study is designed to obtain effect sizes of 2 different CT-P27 treatment groups and placebo group based on the time from the administration of study drug to resolution of influenza symptoms and fever.

For this proof-of-concept dose-ranging study, assuming 90% of subjects are included in the eligible infected population, the total eligible sample size of 164 (63 eligible infected subjects per CT-P27 treatment groups and 38 subjects in placebo group) achieves 80% power to detect 1.8 days of reduction for the primary endpoint of time to resolution with 5% two-sided significance level and standard deviation (SD) of 3 days using a Wilcoxon's rank-sum test.

Considering a dropout rate of 10%, this study will need 183 subjects to be enrolled to achieve 164 evaluable subjects.

For an effect size of 1.5 days of reduction in time to resolution with SD of 2.9 days, the total sample size could be increased to about 250 to achieve at least 80% statistical power with 5% two-sided significance level.

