6.1.1 Diaries

Subjects will be issued a diary on Day 1 and will be required to record the diary from Day 1 to Day 8. The study site staff will instruct the subjects on the use of the diary. Subjects will be told to bring their completed diary each time they return to the study site. Study staff will review the entries in the diary (Flu-iiQ™ questionnaire, recording of body temperature, adverse event and concomitant medication). If the subject is not compliant in regard to filling out the diary (omissions, discrepancies, or other difficulties), instructions on how to use the diary may be repeated. Study site staff should encourage the subject to complete the diary and remind the subject of the importance of following study procedures while at home.

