8.5 Statistical Analyses

8.5.1 Primary Efficacy Analysis

The primary efficacy endpoint analysis will assess the time (in days) from the administration of study drug to resolution of influenza symptoms and fever. This analysis will be performed on the ITTI population. Data will be obtained from responses recorded on the Flu-iiQ™.

Resolution of symptoms has occurred if the following influenza symptoms (as recorded on the Flu-iiQ™) are mild in intensity or none for at least 24 hours.

- Respiratory symptoms (cough, sore throat, and nasal congestion).
- Constitutional symptoms (headache, feeling feverish, body aches and pains, and fatigue).

Resolution of fever is defined as:

- Body temperature of $<37.0^{\circ}\text{C}$ for at least 24 hours. (The start time for resolution of fever is defined as the time recorded in the diary when body temperature was $<37.0^{\circ}\text{C}$ for at least 24 hours.)

If the subject has received the drugs for symptom relief, the effective duration of the drugs for symptom relief should be considered.

For example, the study drug was administered at 12:00 on 1st day. The first time body temperature recorded $<37.0^{\circ}\text{C}$ in the diary was 10:00 on 2nd day and continued more than 24 hours. But acetaminophen/paracetamol known to be effective for 6 hours had been administered at 09:00 on 2nd day [1 hour prior to the time when the body temperature decreased $<37.0^{\circ}\text{C}$], it will be calculated that the start time point for body temperature $<37.0^{\circ}\text{C}$ is 15:00 on 2nd day [27 hours after the study drug administration]. Then, if the next first time body temperature recorded $<37.0^{\circ}\text{C}$ in the diary was 22:00 on 2nd day and body temperature was $<37.0^{\circ}\text{C}$ for 24 hours from then, the start time for resolution of fever is 22:00 on 2nd day [34 hours after the study drug administration].

The primary efficacy endpoint will be analyzed using a Wilcoxon rank-sum test to assess differences between treatment groups, if every subject were followed until resolution of influenza symptoms and fever. The statistically significant difference of time to resolution of influenza symptoms and fever between placebo and CT-P27 based on Wilcoxon rank-sum test will be presented by p-values. If there is any censoring, the primary efficacy endpoint will be analyzed using Log-rank test, and Kaplan-Meier plots will be presented.

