The primary efficacy endpoint will be analyzed using a Wilcoxon rank-sum test to assess differences between treatment groups (CT-P27 45 mg/kg vs placebo, CT-P27 90 mg/kg vs placebo), if every subject is followed until resolution of influenza symptoms and fever. The Wilcoxon rank-sum test will be used to test for a statistical significant difference of time to resolution between placebo and CT-P27. The results of the analysis will be summarized using p-values. The significant level will be set to 5%. If p-value is lower than 5%, it is considered that there is a significant difference between placebo and CT-P27. For subjects who withdrew from the study before the symptoms have resolved or if the symptoms did not resolve until the data cut-off, data will be censored at the latest date/time recorded on the diary or start date/time of study drug administration when there are no recorded data on the diary after study drug administration. If there is any censoring, the primary efficacy endpoint will be analyzed using Log-rank test and Gehans Wilcoxon test, and the result will be presented by p-values from the two tests. Also the table will present count of censoring reasons and 25th percentile, median, 75th percentile of time from administration of study drug to resolution. Kaplan-Meier plots will be presented.

CONFIDENTIAL

Statistical Analysis Plan

If there are no censoring data, sensitivity analysis using tipping point analysis under Missing Not at Random (MNAR) will be also performed to explain varying cases about average unobserved outcomes dropouts on two treatment groups.

Sensitivity Analyses which alter resolution conditions of primary efficacy analysis will be performed on the ITTI population. Following two endpoints will be assessed as described for the primary efficacy endpoint.

- Time (in days) to resolution of influenza symptom (respiratory and constitutional symptoms)

In the analysis, fever is not considered and the definition of resolution of symptom is the same as those of primary efficacy analysis.

- Time (in days) to resolution of influenza symptom and fever

In the analysis, threshold of resolution of fever is changed to 37.8°C and the definition of resolution of symptom is the same as those of primary efficacy analysis.

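### The stated 80% power is for an uncensored rank-sum test; the censored-data analysis that will almost certainly replace it has no stated power and, in the SAP, no deciding test

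*Protocol*

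**What the plan says.** **Power.** Protocol 8.1, repeated in the synopsis and SAP 5.2, says the eligible sample "achieves 80% power to detect 1.8 days of reduction for the primary endpoint of time to resolution". The calculation is for the rank-sum test, two-sided at 5%, and takes the SD as 3 days. The arm sizes are "63 eligible infected subjects per CT-P27 treatment groups and 38 subjects in placebo group". On losses: "Considering a dropout rate of 10%, this study will need 183 subjects to be enrolled to achieve 164 evaluable subjects".

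**Analysis.** SAP 10.1 compares each dose with placebo ("CT-P27 45 mg/kg vs placebo, CT-P27 90 mg/kg vs placebo") by the rank-sum test, but only "if every subject is followed until resolution of influenza symptoms and fever". Protocol 8.5.1 sets the same condition and continues: "If there is any censoring, the primary efficacy endpoint will be analyzed using Log-rank test, and Kaplan-Meier plots will be presented". In the censored case SAP 10.1 reports p-values from both the log-rank test and Gehan's Wilcoxon test. It does not say which one counts, or what follows if they disagree. SAP section 13, which lists changes from the protocol, does not mention Gehan's test. Its entry on added sensitivity analyses fits the altered resolution definitions at the end of SAP 10.1.

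**Follow-up.** Protocol 6.1.1: "Subjects will be issued a diary on Day 1 and will be required to record the diary from Day 1 to Day 8". SAP 10.1 censors subjects who withdraw or do not resolve at their last diary entry, or at dosing if there is none. Diary records kept for a suspicious-ADE assessment also count.

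**The concern.** The power statement and the analysis rule describe different tests. A single censored subject is enough to leave the powered test behind, and neither document gives power for what replaces it.

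Two things are at stake. First, a reader of a non-significant result would assume a 20% chance of missing a true 1.8-day effect, when the protocol's censored-data test may miss it more often. Second, under the SAP two p-values would stand side by side. If one fell below 5% and the other did not, the plan gives no rule for whether the comparison was positive. A power figure has a clear meaning only when it is tied to one named test.

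**Working it through.** **Inputs.** From Protocol 8.1: 63 vs 38, difference 1.8 days, SD 3 days, two-sided 5%, dropout 10%. From SAP 10.1: each dose against placebo. The documents give no distribution, placebo mean or censoring rate. A normal shift and placebo means of 5 to 7 days are therefore assumptions.

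**1. Reproduce the 80%.**
- Standard error: 3 × √(1/63 + 1/38) = 3 × 0.2054 = 0.616. The z for means is 1.8/0.616 = 2.921.
- With rank-sum efficiency 3/π = 0.955: 2.921 × √0.955 = 2.855, and power is Φ(2.855 − 1.960) = 81.4%.
- Noether's formula: Φ(1.8/(3√2)) = 0.664, so z = 0.164 × √(12 × 101 × 0.376 × 0.624) ≈ 2.77, and power is 79.1%.
- Simulation under a normal shift: 80.6%.

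The stated figure is correct for the test it names. The enrolment step also reproduces: 164/0.90 = 182.2, rounded up to 183.

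**2. How likely is censoring?** If each subject has a 5% chance of being censored, the chance that none of the 101 subjects in one comparison is censored is 0.95^101 = 0.6%. At 2% it is 0.98^101 = 13%, or 0.98^164 = 3.6% over all eligible subjects. Day 8 is 168 hours after the infusion starts. Resolution must hold for 24 hours, so a subject who first settles on Day 8 cannot be confirmed from the regular diary alone.

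**3. Power of the censored-data tests.** Normal shift of 1.8 days, SD 3, 63 vs 38. The runs used 2,500 to 20,000 replicates per scenario, so the Monte Carlo standard error is below 0.9 points. Triplets are for placebo means of 5, 6 and 7 days.

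| Follow-up | Censored % | Log-rank % | Gehan % |
|---|---|---|---|
| No censoring | 0 | 74.5 | 79.8 |
| Cut at 14 days | 0.1 / 0.2 / 0.5 | 75.2 / 73.6 / 74.0 | 80.4 / 79.2 / 79.6 |
| Cut at 8 days | 9 / 16 / 25 | 74.0 / 74.2 / 73.2 | 79.0 / 79.0 / 77.5 |
| Cut at 7 days | 16 / 25 / 36 | 73.7 / 73.9 / 72.2 | 78.0 / 77.6 / 76.0 |
| Cut at 8 days + 5% dropout | 12 / 18 / 27 | 75.0 / 73.0 / 73.1 | 80.0 / 77.6 / 77.2 |

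An extreme case, with a hard cut at 7 days and 10% dropout inside that window, gives about 70% for log-rank and about 74-77% for Gehan. Most of the log-rank loss is already present with no censoring. It comes from how that test weights a location shift, and less from lost information.

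**4. Other shapes.** With SD 3 and the same mean difference, log-rank power is about 66-73% for a shifted gamma, 67-88% for gamma or Weibull with SD 3 in both arms, 74-80% for a logistic and 69-94% for a lognormal. Across all the shapes tried, the range is about 65% to above 90%. Under the skewed shapes the rank-sum test itself has 84-99% power, so they do not reproduce the plan's 80%. Gehan's test stays close to the rank-sum value throughout.

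**The case against.** A reader might infer that the test that will run has only about 70-75% power on the plan's own assumptions. The documents do not support that, for three reasons.

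- SAP 10.1 runs two tests under censoring. Gehan's Wilcoxon is the censored-data counterpart of the powered rank-sum test and keeps most of its power.
- The plan assumes a difference and an SD, not a distribution or a placebo mean. Some shapes give log-rank power above 80%.
- The lowest figures need conditions the plan does not state. A hard 7-day cut ignores the suspicious-ADE diaries, which Protocol 6.2.5 starts for symptoms unresolved at Day 8 and which SAP 10.1 uses. Protocol 8.1 calls the 164 evaluable after dropout, and its 10% is not tied to the first week of a 110-day study.

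This stands, and it limits the size of the point. It does not remove it. The extension depends on the investigator's opinion about symptoms, so a subject whose temperature is still 37.0°C or above need not qualify. The ITTI population keeps withdrawn subjects, and SAP 10.1 censors them. Protocol 8.6.1 plans multiple imputation for missing data, but SAP 10.3.1 applies it only to questionnaires with at least one relevant item answered, so it does not fill in follow-up after withdrawal.

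A reader might also infer that the trial depends on 80% power per dose for a go/no-go decision. No such rule is stated. Protocol 8.1 describes the aim as obtaining effect sizes, and Protocol 2.2 says effect size, safety, efficacy and PK will inform later dose selection. Significance at 5% is nevertheless the criterion in SAP 10.1, so the deciding test matters.

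**Conclusion.** The point holds in a limited form. The 80% is arithmetically correct, but only for an uncensored rank-sum test that is very unlikely to be the one used. Under the normal-shift model that yields 80%, with an assumed placebo mean of 5 to 7 days, the protocol's log-rank test has about 72-75% power, a loss of roughly 5 to 8 points. Gehan's test has about 76-80%, a loss of 0 to 4 points. The extreme case lowers these to about 70% and 74-77%. The log-rank figure depends strongly on the assumed shape. The firmer defect is that the protocol and SAP differ on the censored-data analysis, the SAP names no deciding test, and the stated power belongs to neither candidate.

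**What to change.** 1. In Protocol 8.5.1 and SAP 10.1, name one deciding test for the censored case before unblinding and report the other as supportive. Gehan's Wilcoxon is closest to the test that was powered.
2. Record in SAP section 13 that Gehan's test was added and what role it has.
3. In Protocol 8.1, the synopsis and SAP 5.2, restate power for the deciding test. Give the assumed distribution, placebo mean, diary limit (with the suspicious-ADE extension) and dropout before resolution. Label 80% as the uncensored rank-sum value.

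The cost is wording and one simulation, and the stated power becomes slightly less favourable. Enrolment need not change. For scale, under a normal shift 80% log-rank power would need about 44 + 2 × 73 = 190 eligible subjects in place of 164, which is a further reason to settle the choice of test explicitly.

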Objectives:	
Primary Objective:
 
 To evaluate efficacy as determined according to the time to resolution of respiratory and constitutional symptoms of influenza and fever 
Secondary Objectives
 
 To evaluate the additional efficacy and safety of CT-P27, including potential effects on the incidence of antibody-dependent enhancement (ADE) 
Exploratory Objectives:
 
 To assess the pharmacokinetics (PK) of CT-P27 components (CT-P22 and CT-P23) To assess immunogenicity To assess the characterization of isolated influenza viruses 		
Sample Size:	Approximately 183 subjects with acute uncomplicated influenza A infection will be randomly assigned to the 45 mg/kg CT-P27, 90 mg/kg CT-P27 or placebo groups (70 subjects per CT-P27 treatment groups and 43 subjects in placebo group).		
Main Selection Criteria:	Male or female subjects with a diagnosis of influenza A by a rapid influenza diagnostic test and onset of illness no more than 48 hours prior to the planned administration of study drug will be considered for enrollment in the study if they meet all of inclusion criteria and none of the exclusion criteria.		
Inclusion Criteria:	
Each subject must meet all the following criteria to participate in this study:
 
 Subject is a male or female and aged 19 to 64 years, inclusive. Subject can voluntarily provide a written informed consent. Onset of illness no more than 48 hours prior to the planned administration of study drug. If the adjustments of visit schedule is required, additional 12 hours can be allowed (Maximum onset of illness: 60 hours). 		

Note: time of onset of illness is defined as the earlier of either (a) the time when the body temperature was first measured as $\geq 38.0^{\circ}\text{C}$ ($\geq 100.4^{\circ}\text{F}$) or (b) the time when the subject experienced the presence of at least two symptoms that are respiratory and/or constitutional (moderate to severe in intensity).

4. As reported by the subject and recorded on the Flu-iiQ™ completed at screening, the subject has at least two of the following symptoms (moderate to severe in intensity):
 - a) Respiratory symptom (cough, sore throat, or nasal congestion) or
 - b) Constitutional symptom (headache, feeling feverish, body aches and pains, or fatigue).

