4.3.3 Disease Diagnostic Criteria

The subjects will be screened for the presence of influenza A using a rapid influenza diagnostic test no more than 24 hours before treatment with study drug. The presence of influenza A will

be confirmed with qPCR or cell culture in only enrolled subject. Subjects who are positive for influenza A on the rapid influenza diagnostic test but negative on qPCR or cell culture will continue in the study and be followed up for safety purposes.

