4.3.4 Subject Withdrawal

All subjects are free to withdraw from participation in the study at any time, for any reason, specified or unspecified, and without prejudice to further treatment. If a subject chooses to withdraw from the study, they will be encouraged to return to the site for safety reasons to complete the assessments planned for EOS visit

The Investigator will ensure that all reasonable attempts (telephone calls, contact with primary care physician, certified letter) are made to obtain follow-up safety information on subjects who do not return to the site for study visits or are lost to follow-up.

Subjects who are withdrawn from the study after randomization will not be replaced.

Subjects who withdraw from the study after dosing will be advised by the Investigator to continue contraception restrictions for 5 months after the administration of study drug.

The Investigator will ensure that the reasons for withdrawal are documented on the subject's medical records (source documents) and in the electronic Case Report Form (eCRF). If the subject withdraws due to an AE, the details of the AE must be entered on the AE section of the eCRF. If the reason for subject withdrawal is not known, the subject must be contacted and followed up in order to establish whether the reason for withdrawal was an AE, and if so, this must be reported in accordance with the procedures outlined in [Section 6.2.1.5](#).

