8.4.2 Intent-to-Treat Infected Population

The intent-to-treat infected (ITTI) population is defined as all randomized subjects with confirmed influenza A by qPCR or cell culture. The primary and secondary efficacy endpoint analysis, the genotype and phenotype analysis will all be performed on the ITTI population.

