8.6.1 Missing Data

Missing data from subjects who withdraw from the study, including AEs and any follow-up, will be included in the primary endpoint analysis in the ITTI population. Assuming Missing at Random (MAR), multiple imputation will be the primary imputation method for handling the missing data. Sensitivity analysis using tipping point analysis under Missing Not at Random (MNAR) will be also accessed for the primary endpoint analysis in the ITTI population.

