5.2 Determination of Sample Size

This study is designed to obtain effect sizes of 2 different CT-P27 treatment groups and placebo group based on the time from the administration of study drug to resolution of influenza symptoms and fever.

For this proof-of-concept dose-ranging study, assuming 90% of subjects are included in the eligible infected population, the total eligible sample size of 164 (63 eligible infected subjects per CT-P27 treatment groups and 38 subjects in placebo group) achieves 80% power to detect 1.8 days of reduction for the primary endpoint of time to resolution with 5% two-sided significance level and SD of 3 days using a Wilcoxon's rank-sum test.

Considering a dropout rate of 10%, this study will need 183 subjects to be enrolled to achieve 164 evaluable subjects.

For an effect size of 1.5 days of reduction in time to resolution with SD of 2.9 days, the total sample size could be increased to about 250 to achieve at least 80% statistical power with 5% two-sided significance level.

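### The sample-size text names two 10% losses but allows for one: 183 enrolled gives about 164 confirmed infected, and the 80% power is stated at that number with nothing set aside for dropout

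*Protocol*

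**What the plan says.** The same sample-size text appears in the Protocol synopsis (Sample Size Assumptions), Protocol 8.1 and SAP 5.2. It makes two assumptions, one after the other.

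- Infection: "assuming 90% of subjects are included in the eligible infected population, the total eligible sample size of 164", split as 63 per CT-P27 group and 38 on placebo. This size is said to give 80% power for a 1.8-day reduction, with SD 3 days, a two-sided 5% level and a Wilcoxon rank-sum test.
- Dropout: "Considering a dropout rate of 10%, this study will need 183 subjects to be enrolled to achieve 164 evaluable subjects".

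The planned enrolment is "70 subjects per CT-P27 treatment groups and 43 subjects in placebo group", which is 183 in total.

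Other sections bear on how the two losses act:

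- Protocol 4.3.3: subjects positive on the rapid test but "negative on qPCR or cell culture will continue in the study and be followed up for safety purposes".
- Protocol 4.3.4: "Subjects who are withdrawn from the study after randomization will not be replaced".
- Protocol 8.4.2: the ITTI population, on which the primary endpoint is analysed, is "defined as all randomized subjects with confirmed influenza A by qPCR or cell culture".
- Protocol 8.6.1: missing data from subjects who withdraw "will be included in the primary endpoint analysis in the ITTI population", with multiple imputation as the main method. SAP 10.1 instead censors subjects who withdraw before resolution.

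**The concern.** A reader of this paragraph expects two reductions between enrolment and analysis: some subjects prove not to be infected, and some of the infected drop out. The step from 164 to 183 has room for one. The text labels the 164 both as eligible infected and as evaluable after dropout, and with 183 enrolled it cannot be both unless the two losses are the same one. No passage says that they are. The rest of the Protocol treats them as different events: an unconfirmed subject stays in follow-up, and a withdrawn subject leaves and is not replaced.

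At stake is what the 80% means. This paragraph is the only justification given for the size of the trial, and the effect size it yields is meant to inform later studies. As written, a reader cannot tell whether the power is quoted before or after dropout.

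**Working it through.** **Inputs.** From Protocol 8.1: 90% infected, 10% dropout, 164 = 63 + 63 + 38, difference 1.8 days, SD 3 days, two-sided 5%, rank-sum test. From the synopsis: 183 = 70 + 70 + 43. Assumption needed for the power check: normally distributed times, for which the rank-sum test has relative efficiency 3/π = 0.955 against the t test.

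**1. Reproduce the enrolment figure.**
- Total: 164/0.9 = 182.2, rounded up to 183.
- By arm: 63/0.9 = 70; 38/0.9 = 42.2, rounded up to 43. Sum: 70 + 70 + 43 = 183.

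One division by 0.9 gives the stated figures exactly.

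**2. Apply the infection loss to the planned enrolment.**
- 70 × 0.9 = 63; 43 × 0.9 = 38.7; 183 × 0.9 = 164.7.

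The infection loss alone brings 183 down to the stated 63/63/38, so nothing is left in the 183 for dropout.

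**3. Reproduce the power.** Multiply each arm by 3/π and use the noncentral t distribution, with λ = δ / (SD × √(1/a + 1/b)) and a + b − 2 degrees of freedom.
- 63 vs 38: a = 60.2, b = 36.3, λ = 2.855, 94.4 degrees of freedom, power 80.7%.
- Simulated rank-sum tests on normal data gave 79.9% (20,000 datasets, continuity-corrected) and 80.6% (40,000 trials).

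The stated 80% therefore belongs to 63 vs 38, all contributing in full.

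**4. How much margin is there?** Scaling both arms by 0.98 in the same formula gives 79.9%. An effective loss of about 2% is enough to reach the 80% line.

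**5. Lower bound: a further 10% contributing nothing.**
- 183 × 0.9 × 0.9 = 148.2. By arm, 70 × 0.81 = 56.7 and 43 × 0.81 = 34.8, or about 57/57/35 (which sums to 149 through rounding).
- 57 vs 35: a = 54.4, b = 33.4, λ = 2.730, 85.9 degrees of freedom, power 77.0% (76.8% at the unrounded 56.7 vs 34.83).
- The corresponding simulations gave 76.9% and 76.5%.
- The difference detectable with 80% power moves from 1.785 to 1.868 days, which is 0.083 days or about 2 hours.

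**The case against.** The strongest reply is that no printed figure is wrong. The totals and the arm sizes close exactly if the 90% infected and the 10% dropout are one allowance described from two sides, and the text does use eligible and evaluable for the same 164. This may be what the sponsor meant. It would make 183 right, but the paragraph presents two separate assumptions and nothing in either document merges them. It would need to be said.

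The second reply is that a second loss of subjects does not happen in the planned primary analysis. ITTI is defined by laboratory confirmation only, and withdrawn subjects remain in it by imputation (Protocol 8.6.1) or censoring (SAP 10.1). This stands, and it limits the point. It rules out two readings that a reader might infer:

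- That the trial is under-enrolled and needs 164/0.81 = 202.5, so 203 subjects. This would follow only if withdrawals were removed from the primary analysis, and no section removes them.
- That the power of the trial is 77%. That figure treats dropouts as contributing nothing. Subjects who resolve before leaving contribute in full, and censored subjects contribute the time observed. The scheduled diary covers Days 1 to 8 while follow-up runs to Day 110, so a late withdrawal may cost the primary endpoint nothing.

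The same reply also shows that the dropout sentence gives the wrong reason for 183. If withdrawals stay in ITTI, it is infection confirmation, not dropout, that takes 183 to 164.

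A reader might also infer that the alternative scenario ("the total sample size could be increased to about 250 to achieve at least 80% statistical power") misses its target. The documents do not support this. They give no allocation for the 250 and do not say whether it counts enrolled or eligible subjects. The target would be missed only if 250 meant enrolled and both losses removed subjects, and the second condition conflicts with the ITTI rules. What remains is a missing label.

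**Conclusion.** The point holds as a fault in the stated basis for size and power. Two 10% losses are named and one is applied. With 183 enrolled, about 164 are expected in ITTI, and the 80% (80.7% recomputed) refers to that number with no dropout. Dropout leaves the ITTI count near 164 but reduces information, so the 80% holds only if that reduction is negligible. With 10% dropout, power lies between about 81% and about 77%; the lower end is a bound.

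This rests on normally distributed times, dropout spread evenly over the arms and unrelated to outcome, and the rank-sum test. If any subject is censored, Protocol 8.5.1 moves to the log-rank test and SAP 10.1 to log-rank plus Gehan's Wilcoxon, so the rank-sum figures are then only a guide. The effect is modest, at most about 4 percentage points, and it does not call the enrolment target into question.

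**What to change.** In the Protocol synopsis, Protocol 8.1 and SAP 5.2:

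1. State that 183 enrolled (70/70/43) with 90% confirmed infected gives about 164 (63/63/38) expected in ITTI, and that the 80% power refers to this number before any dropout.
2. Replace the sentence that derives 183 from dropout with one of two statements: that a single 10% allowance covers both losses; or that withdrawals stay in ITTI and 10% dropout could lower rank-sum power from about 81% to no less than about 77%.
3. At most, add one word saying whether the 250 in the alternative scenario means enrolled or eligible.

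The cost is wording in three places. Enrolment, populations, endpoint and tests do not change. The only downside is that the stated power may look slightly less favourable.
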